### **3.5 Analysis sets**

#### **3.5.1 Enrolled Set**

The Enrolled Set (ES) will consist of all subjects who have given informed consent.

#### **3.5.2 Randomized Set**

The Randomized Set (RS) will consist of all randomized subjects.

#### **3.5.3 Safety Set**

The Safety Set (SS) will consist of all subjects that received at least 1 dose of IMP.

#### **3.5.4 Full Analysis Set**

The Full Analysis Set (FAS) will consist of all subjects in the RS that receive at least 1 dose of the IMP and have a valid PASI measurement at Baseline.

#### **3.5.5 Maintenance Set**

The Maintenance Set (MS) will consist of all subjects that receive at least 1 dose of IMP at Week 16 or later in the double-blind Treatment Period (including the Week 16 dose).

#### **3.5.6 Open-Label Set**

The Open-label Set (OLS) will consist of all subjects that received at least 1 dose of bimekizumab at Week 48 or later in the OLE Period (including the Week 48 dose).

### **3.5.7 Open-Label Set 2**

The Open-label Set 2 (OLS2) will consist of all subjects that received at least 1 dose of bimekizumab at Week 144/OLE2 Baseline Visit or later in the OLE2 Period.

### **3.5.8 Per Protocol Set**

The Per-Protocol Set (PPS) will consist of all subjects in the RS who had no important protocol deviations affecting the primary efficacy variable. Important protocol deviations will be predefined and subjects with important protocol deviations will be evaluated during ongoing data cleaning meetings prior to unblinding of the data.

### **3.5.9 Pharmacokinetics Per-Protocol Set**

The Pharmacokinetics Per-Protocol Set (PK-PPS) consists of all randomized subjects who received at least 1 dose of the IMP and provided at least 1 quantifiable post-dose plasma concentration without important protocol deviations that would affect the concentration.

### **3.5.10 Bimekizumab Set**

The Bimekizumab Set (BKZ Set) consists of all randomized subjects who received at least 1 dose of bimekizumab in the double-blind or Open-Label extension treatment period.

## **3.6 Treatment assignment and treatment groups**

It is expected that subjects receive treatment as randomized and hence safety analyses will be based on the SS, as randomized. However, if after unblinding it is determined that subjects randomized to a treatment arm had never received such treatment, then for safety analysis, these subjects will be reallocated to the appropriate received treatment groups, unless otherwise specified.

If subjects randomized to secukinumab received bimekizumab at any time, then for safety analyses these subjects will be reallocated to the appropriate bimekizumab treatment group, unless otherwise specified. Subjects randomized to bimekizumab will only be reallocated to the secukinumab treatment group if they never received bimekizumab.

Efficacy analyses should be performed according to randomized treatment and not actual treatment received.

Randomized treatment groups are Bimekizumab 320mg Q4W and Secukinumab 300mg Q4W. Maintenance treatment groups are Bimekizumab 320mg Q4W, Bimekizumab 320mg Q8W, and Secukinumab 300mg Q4W.

Re-randomized (Open-Label extension) treatment groups are Bimekizumab 320mg Q4W and Bimekizumab 320mg Q8W. Unless otherwise specified, the OLE period will be summarized by treatment sequence comprising randomized treatment at Baseline and OLE period treatment at Week 48.

The following treatment sequences will be used to summarize efficacy data and specific safety data related to laboratory, ECG, PHQ-9, eC-SSRS, and vital signs assessments:

- Subjects receiving bimekizumab in the double-blind treatment period:
  - Initiating OLE on bimekizumab Q8W

- 
- Initiating OLE on bimekizumab Q4W
  - Subjects receiving secukinumab in the double-blind treatment period
    - Initiating OLE on bimekizumab Q8W
    - Initiating OLE on bimekizumab Q4W
  - All Subjects

Adverse event data (including for a subgroup of subjects who switched from Q4W to Q8W during OLE period) and study compliance data will be summarized in 2 treatment groups based on the dose most recently received prior to the date of the event or assessment

- Bimekizumab 320mg Q8W
- Bimekizumab 320mg Q4W
- Bimekizumab Total

In addition, the following key efficacy variables:

- PASI90 response
- PASI100 response
- IGA Clear or Almost Clear (with at least a 2-category improvement from Baseline)
- IGA Clear (with at least a 2-category improvement from Baseline)

will be summarized for the Open-Label Extension treatment period by the following randomized treatment sequences:

- Bimekizumab Q4W/Q8W/Q4W for non-responder at Week 48 (<PASI90)
- Bimekizumab Q4W/Q4W/Q4W for non-responder at Week 48 (<PASI90)
- Secukinumab / Bimekizumab Q4W for non-responder at Week 48 (<PASI90)
- Bimekizumab Q4W/Q8W/Q8W for responder at Week 48 (>=PASI90)
- Bimekizumab Q4W/Q4W/Q8W for responder at Week 48 (>=PASI90)
- Bimekizumab Q4W/Q4W/Q4W for responder at Week 48 (>=PASI90)
- Secukinumab / Bimekizumab Q8W for responder at Week 48 (>=PASI90)
- Secukinumab / Bimekizumab Q4W for responder at Week 48 (>=PASI90)

Safety and efficacy assessments for the OLE2 period will only include subjects who entered the OLE2 period and will be summarized based on OLS2, by the assigned treatment as follows:

- Subjects who enroll directly from the OLE treatment period: Group A
  - Bimekizumab Q8W Group A
- Subjects in Group B who reinitiate bimekizumab after having completed treatment in the OLE and have an IGA <3 upon entry to the OLE2: Group B
  - Bimekizumab Q8W Group B

- Subjects in Group B who reinitiate bimekizumab after having completed treatment in the OLE and have an IGA  $\geq 3$  upon entry to the OLE2: Group B
  - Bimekizumab Q4W/Q8W Group B
- For safety summaries only
  - BKZ Total.

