### 2.3.2.4 OLE Period

After completion of the Week 48 visit assessments, subjects will be allowed to enroll in the OLE Period. All subjects enrolling in the OLE Period will sign a new ICF, and then receive the following IMP regimens as determined by the subject's treatment regimen and PASI response in the double-blind Treatment Period.

At Week 48, subjects receiving:

- Bimekizumab 320mg Q4W who achieve PASI90 at Week 48 of the double-blind Treatment Period will be randomized 1:1 to receive bimekizumab 320mg Q4W or bimekizumab 320mg Q8W.
- Bimekizumab 320mg Q4W who do not achieve PASI90 at Week 48 of the double-blind Treatment Period will receive bimekizumab 320mg Q4W.
- Bimekizumab 320mg Q8W who achieve PASI90 at Week 48 of the double-blind Treatment Period will receive bimekizumab 320mg Q8W.
- Bimekizumab 320mg Q8W who do not achieve PASI90 at Week 48 of the double-blind Treatment Period will receive bimekizumab 320mg Q4W.

- Secukinumab who achieve PASI90 at Week 48 of the double-blind Treatment Period will be randomized 1:1 to receive bimekizumab 320mg Q4W or bimekizumab 320mg Q8W.
- Secukinumab who do not achieve PASI90 at Week 48 of the double-blind Treatment Period will receive bimekizumab 320mg Q4W.

From Week 64 the subjects who are receiving bimekizumab 320mg Q4W at the time of implementation of protocol amendment 5.0 will have their dosing interval changed to bimekizumab 320mg Q8W at the next clinical site assessment as described on [Table 7–2](#) for subjects who are receiving bimekizumab 320mg Q4W and have reached Week 96 prior to the implementation of Protocol Amendment 5.0, if PASI90 is achieved, the subject's dosing interval will change from 320mg Q4W to 320mg Q8W (default), unless, based on medical judgment, the Investigator decides differently. Otherwise, if PASI90 is not achieved they will have their dosing interval changed to bimekizumab 320mg Q8W at the next clinical site assessment after implementation of protocol amendment 5.0 as detailed above.

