**Table 7-2: Dosing scheme, OLE Period**

Week	48 (1st OLE dose)	Year 2											Year 3													
		52	56	60	64 ab	68	72 ab	76	80	84 ac	88	92	96 ab	100	104	108 ac	112	116	120 ab	124	128	132 ac	136	140		
Bimekizumab 320mg Q4W	●●	●●	●●	●●	●●	●●	●●	●●	●●	●●	●●	●●	●●	●●	●●	●●	●●	●●	●●	●●	●●	●●	●●	●●	●●	●●
Bimekizumab 320mg Q8W	●●		●●		●●		●●		●●		●●		●●		●●		●●		●●		●●		●●		●●	

OLE=Open-Label Extension; Q4W=every 4 weeks; Q8W=every 8 weeks

Notes: A bimekizumab 160mg injection is depicted by a black circle (●).

a The subject's dosing interval will change from Q4W to Q8W at Week 64 or at the next scheduled clinic visit after implementation of Protocol Amendment 5.0 if the subject has already completed the Week 64 visit.

b Subjects whose dosing interval is changed to Q8W should be dosed at this visit and will receive kits for home administration 8 weeks later.

c Subjects whose dosing interval is changed to Q8W should NOT be dosed at this visit and will receive kits for home administration 4 weeks later.

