#### 10.1.4.1 For subjects who do not switch study treatments

Study medication duration (days)

- For subjects who receive Q4W in the Open-Label Extension Period (subjects who discontinue prior to switching to Q8W):
  - Date of last bimekizumab dose in the Open-Label Extension Period – date of first dose in the Open-Label Extension Period + 28 days (for subjects on Q4W dosing)
- For subjects who receive Q8W in the Open-Label Extension Period use the minimum of:
  - Date of last bimekizumab dose in the Open-Label Extension Period – date of first dose in the Open-Label Extension Period + 56 days
  - First dose date in Open-Label Extension 2 Period – date of first dose in the Open-Label Extension Period + 1

Note: If date of last bimekizumab dose in the Open-Label Extension Period + 28 days (or 56 days for subjects on Q8W dosing) extends to a date beyond the final visit date (including PEOT, but not including SFU), then this calculation reverts to:

- Final visit date (including PEOT, but not including SFU) – date of first dose in the Open-Label Extension Period + 1.

Note: For subjects who die, if date of last bimekizumab dose in the Open-Label Extension Period + 28 days (or 56 days for subjects on Q8W dosing) extends to a date beyond the date of death, then this calculation reverts to:

- Date of death – date of first dose in the Open-Label Extension Period + 1.

Time at risk (days)

- For all subjects, use the minimum of the following:
  - Date of last dose in the Open-Label Extension Period – date of first dose in the Open-Label Extension Period + 140 days,
  - Date of first dose in OLE2 - date of first dose in the Open-Label Extension Period + 1 day
  - Date of last clinical contact in OLE and SFU – date of first dose in the Open-Label Extension Period + 1.
  - Date of death – date of OLE first dose

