The following summary will be provided by treatment for the Initial and Maintenance Treatment Period (combined) for the SS (only subjects treated with BKZ, only Total BKZ will be summarized):

- Incidence of TEAEs per 100 subject years by SOC, HLT, and PT and by Time of Onset Relative to Anti-bimekizumab Antibody Status

Incidence of TEAEs per 100 subject years by SOC, HLT, and PT and by Time of Onset Relative to COVID-19 pandemic (prior to COVID-19 pandemic, during COVID-19 pandemic).

The following summaries will be provided by treatment for the Initial Treatment Period (SS) as well as for Initial and Maintenance Treatment Period combined (SS):

- Incidence of TEAEs Above Reporting Threshold of 5% with Risk Differences by SOC and PT
- Incidence of Serious TEAEs and Risk Differences by SOC and PT

The tables with risk differences will also be accompanied by figures (dot plots) which show the incidence of the adverse events and corresponding 95% risk difference confidence intervals. These will be ordered by descending order of risk difference (bimekizumab vs secukinumab).

The following selected AEs summaries will be provided separately for the Open-Label Extension Period. Separate AEs summaries will be provided for the OLE2 treatment period by treatment sequence as described in Section 3.6 and will be based on the OLS2:

- Incidence of COVID-19 TEAEs
- Incidence of TEAEs Overview
- Incidence of TEAEs per 100 Subject-Years
- Incidence of Serious TEAEs per 100 Subject-Years
- Incidence of Serious TEAEs by Relationship
- Incidence of TEAEs Leading to Discontinuation per 100 subject-years
- Incidence of TEAEs Leading to Death
- Incidence of Non-Serious TEAEs Above Reporting Threshold of 5% by SOC and PT
- Incidence of Non-Serious TEAEs Above Reporting Threshold of 5% by Relationship SOC and PT

In addition, the following AEs summaries will be provided for the Open-Label Extension Periods only, by treatment at the time of AE onset, and will be based separately on the OLS and OLS2.

- Incidence of TEAEs Excluding TEAEs Exclusively Related to COVID-19 Vaccine by SOC, HLT, and PT
- Incidence of TEAEs Exclusively Related to COVID-19 Vaccine by SOC, HLT, and PT
- Incidence of COVID-19 Vaccine Interval Censored TEAEs by SOC, HLT, and PT
- Incidence of COVID-19 Vaccine Interval TEAEs by SOC, HLT, and PT

The following listings will be provided separately for the OLS and OLS2:

- Listing of TEAEs Related to COVID-19 Vaccine

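### Adverse events in the OLE subgroup that switched from Q4W to Q8W are split by dose, but its Q4W column leaves out everyone who died or stopped before the switch

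*SAP*

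**What the plan says.** SAP Section 3.6 states that "Adverse event data (including for a subgroup of subjects who switched from Q4W to Q8W during OLE period"), together with compliance data, "will be summarized in 2 treatment groups based on the dose most recently received prior to the date of the event or assessment". The columns are Q8W, Q4W and bimekizumab total.

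A subject enters the switch subgroup by one of two routes, and both require the subject to be still on Q4W:
- In Table 7-2 (footnote a) the rule reads: "The subject's dosing interval will change from Q4W to Q8W at Week 64 or at the next scheduled clinic visit after implementation of Protocol Amendment". The amendment meant is 5.0, and the later visit is for subjects already past Week 64.
- Section 2.3.2.4: for subjects on Q4W who "have reached Week 96 prior to the implementation of Protocol Amendment 5.0, if PASI90 is achieved", the interval changes by default unless the investigator decides otherwise.

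Subjects who never get that far are dealt with in Section 10.1.4.1, on non-switchers, which identifies those receiving Q4W in the OLE as "subjects who discontinue prior to switching to Q8W".

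Section 10.1.4.2 ends switchers' Q4W time at risk at the first Q8W dose, with no term for death, last contact or 140 days of follow-up. Their Q8W time at risk has all three.

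Section 10.2.2 lists the OLE outputs, among them "Incidence of TEAEs Leading to Discontinuation per 100 subject-years", serious events and events leading to death. It does not say which of these will be produced for the switch subgroup. Section 3.6 attaches no landmark, restriction or caution to the subgroup.

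**The concern.** The subgroup is defined by something that happens later, and the time before that event is then reported as Q4W experience. Every member is guaranteed to be alive and on treatment throughout the pre-switch time. This is immortal-time selection: the Q4W column is conditional on having tolerated Q4W long enough to switch, and the Q8W column carries no equivalent condition.

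A reader wanting to know whether the Amendment 5.0 interval change was safe would naturally compare the two columns. With identical true risk on both regimens, more subjects would appear with discontinuation-related, fatal and probably serious events after the change than before it.

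**Working it through.** The SAP states no figure for this subgroup, so there is none to reproduce. The exclusion follows from the definitions; its size needs assumed rates.

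**Who can appear where**

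| Subject's course in the OLE | In the switch subgroup? | Column |
|---|---|---|
| Event on Q4W, dies or stops before any Q8W dose | No (Section 10.1.4.1) | None |
| Event starts on Q4W, stops or dies after first Q8W dose | Yes | Q4W |
| Event starts on the switch date | Yes | Q4W, apart from the exceptions in Section 10.2 |
| Event starts on Q8W, stops or dies | Yes | Q8W |

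The first row is the missing group. The second and third show that the Q4W discontinuation and death rows need not be exactly zero.

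**Size with a correct denominator.** Assume constant, independent rates per 100 patient-years on Q4W: s for events that end treatment, o for other events.
- All subjects while on Q4W: o + s
- Switchers while on Q4W: o, because requiring that no stop occurred before the switch removes s
- Ratio: o / (o + s)

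The SAP gives neither rate. Assumed: s = 1, 3, 6; o = 150 (all events) or 5 (an uncommon event type).

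| s | o = 150 | o = 5 |
|---|---|---|
| 1 | 150/151 = 99.3% | 5/6 = 83.3% |
| 3 | 150/153 = 98.0% | 5/8 = 62.5% |
| 6 | 150/156 = 96.2% | 5/11 = 45.5% |

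A simulation of 400,000 subjects, with switches at Weeks 64, 72, 84, 96, 108 or 120, gave 99.3, 98.0 and 96.2%, and 83.1, 62.0 and 44.9%. The deficit is thus about 1 to 4% for all events and about 17 to 55% for an uncommon type that often ends treatment.

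For serious events, let R be the true rate and f the share that leads to stopping. Switchers then show about R(1 − f) on Q4W. With an assumed R = 6, this is 5.4 at f = 10%, 4.2 at 30% and 3.0 at 50%. The answer is the assumed f restated, and the SAP gives no f.

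**Denominator as written.** Section 10.1.4.2 counts switchers' Q4W time at risk from the last Q4W dose to the first Q8W dose, plus 1 day. The medication-duration formula in the same section and the Bimekizumab Set rule in Section 10.1.5.2 both start at the first Q4W dose. With a 28-day gap between last Q4W and first Q8W dose:
- As written: 28 + 1 = 29 days
- From the first OLE dose, switch at Week 64: (64 − 48) × 7 + 1 = 113 days; 113/29 = 3.9
- Switch at Week 120: (120 − 48) × 7 + 1 = 505 days; 505/29 = 17.4

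Under Table 7-2, footnote c, a switch at the Week 84 visit puts the first Q8W dose at Week 88, after a last Q4W dose at Week 80: 281/57 = 4.9, inside that range.

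Taken literally, the formula inflates non-zero Q4W rates by more than the selection lowers them, even at the largest deficit and smallest inflation above: 0.455 × 3.9 = 1.8.

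**The case against.** The strongest objections, and what stands of each:

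- **The table is barely specified.** It rests on a parenthesis in Section 3.6. The switch-specific outputs listed in Section 10.2.2 concern subjects moving from secukinumab to bimekizumab. This stands: that discontinuation or death rows will be shown for Q4W-to-Q8W switchers is not stated. But Section 3.6 does plan the summary by dose and excludes no event type.
- **Sound tables are already planned.** The full Open-Label Set and Bimekizumab Set tables by treatment at onset keep the early stoppers. This stands and limits the damage to the subgroup.
- **No formal comparison of Q4W with Q8W is planned.** Adverse-event risk differences are bimekizumab against secukinumab only. This stands, but side-by-side columns invite the comparison.
- **Q8W follow-up of 140 days.** Those days are also in the Q8W time at risk, so they do not by themselves raise a rate.

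A reader might infer that the subgroup's Q4W rates are too low by construction, or that its Q4W discontinuation and death rows must be zero. The SAP does not support either. Events starting on Q4W can lead to stopping or death after the first Q8W dose, and Section 10.1.4.2 as written pushes exposure-adjusted rates upward. Nor does the SAP describe this subgroup as its test of the interval change.

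**Conclusion.** The selection is real and follows from the definitions without assumed figures: the subgroup's Q4W column omits every event that ended treatment or life before the first Q8W dose, and its Q8W column omits none on that ground. Subject counts read as Q4W against Q8W are biased against Q8W for discontinuation-related and fatal events. For serious events the bias grows with the share leading to stopping, which is unknown here. For all treatment-emergent events it is about 1 to 4% under the assumed rates.

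No single direction can be claimed for exposure-adjusted rates while the Section 10.1.4.2 formula stands, since it acts the other way. That is a separate defect, and correcting it does not bring back the excluded subjects. The matter is worth fixing before the tables are produced, but it does not touch the main safety tables through this exclusion.

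**What to change.** In Section 3.6 and the table shell:
- For the switch subgroup, report post-switch (Q8W) events and rates only.
- Take the Q4W reference from the planned Q4W column of all Open-Label Set subjects while on Q4W, including those who stopped before switching.
- Show no Q4W discontinuation or death rows within the switch subgroup. If a pre-switch column is kept, label it as conditional on reaching the switch.

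Separately, correct Section 10.1.4.2 so that switchers' Q4W time at risk starts at their first Q4W dose in the OLE. Do this first: the same formula supplies the switchers' share of the Open-Label Set Q4W denominator, so the reference rates need it too.

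The cost is SAP wording and one table shell; no new data are needed. The downside is that the two columns no longer hold the same subjects, and the Q8W column remains limited to those who stayed on Q4W until the switch. A footnote should say so.

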### 3.7 Center pooling strategy

Centers will be pooled into regions for analysis purposes. Geographic regions will be categorized as North America, Western Europe, Central/Eastern Europe, and Asia/Australia. Below is a table of geographic regions with corresponding countries.

Region	Countries
North America	Canada, United States
Western Europe	Belgium, France, Germany, Netherlands, Spain, United Kingdom
Central /Eastern Europe	Poland
Asia/Australia	Australia, Turkey

For a sensitivity analysis to test center-by-treatment interaction (see Section 8.1.3.6), the following center pooling algorithm might be used for each geographic region:

- If a center has 10 or more subjects, then no pooling will be done for that center.
- Centers with fewer than 10 subjects will be ordered from largest to smallest with pooling proceeding in the following manner:
  - Two or more centers will be combined until the cumulative subject total is at least 10.
  - Once a pooled center has at least 10 subjects, the process will continue in an iterative fashion for the subsequent centers in the ordered list, where a new pooled center begins each time at least 10 subjects has been reached in the previous pool.
  - If this iterative process reaches the end of the ordered list of centers where the final pooled center has fewer than 10 subjects, then the subjects from the centers in that pool will be combined with the pooled center formed in the previous iteration.

This procedure is only to be performed within a geographic region –there will be no pooling of centers across regions.

In the event that the percentage of randomized subjects is less than 10% in either of the Asia/Australia or Western Europe region, the two regions will be combined as a geographic region stratum for all efficacy modeling, so that there are no modeling convergence issues across efficacy variables.

### 3.8 Coding dictionaries

All medications other than study drug will be classified by WHO Anatomical Therapeutic Chemical (ATC) Classification, presenting Anatomical Main Group (ATC Level 1),

Pharmacological Subgroup (ATC level 3), and preferred term, using World Health Organization Drug Dictionary (WHO-DD) version SEP/2015 for Week 48 and Week 96 analysis, and version MAR 2021 for Week 144 and Final analysis, according to UCB standard operating procedures (SOP).

All AEs will be classified by primary system organ class (SOC), high level term (HLT) and preferred term (PT) using version 19.0 of Medical Dictionary for Regulatory Activities (MedDRA®) according to UCB SOPs.

Previous and ongoing medical history will be classified by version 19.0 of MedDRA® SOC and PT.

